Newcastle Hospitals will provide data from REDCap to Newcastle University as Sponsor. Access to final datasets downloaded from REDCap and from the other study databases will be restricted to members of the study team and collaborators involved in data analyses. Such final datasets will be pseudo-anonymised and will not contain any direct personal identifiers.

The ISF will be held in a secure area at site with access restricted to the study team only. An electronic version of this log may also be held securely on NHS computer systems at site. The TMF will be held securely by the CI at the WCMR with access restricted to authorised team members and Sponsor representatives only.

Access to Data

Direct access to study data including source data contained in the participant's medical notes and elsewhere will be granted to authorised representatives of the Sponsor (Newcastle University), Newcastle Hospitals, or regulatory authorities for the purposes of monitoring, audit, or inspection. Consent for this will be obtained from participants during recruitment.

Following completion of the study, anonymised sets of raw data may be made available for 3rd party research purposes with the appropriate data transfer procedures.

Archiving

Archiving will be authorised by the Sponsor following submission of the end-of-study reports to REC and funder. Responsibility for archiving the ISF will sit with the study site and will be performed as per site SOPs. The TMF will be archived by Newcastle University according to the relevant University requirements.

Essential documents will be archived for a period defined by Sponsor. Destruction of essential documents following the required period of archiving will require sponsor authorisation.

De-identified (pseudo-anonymised) study data extracted from the study databases will be retained following the end of the study for further analysis. This data will be held securely on Newcastle University servers for up to 20 years.

Data collected and held on REDCap will be archived and destroyed at the direction of Sponsor and in accordance with the relevant NJRO SOPs for this.

Indemnity

Newcastle University has in place a Public Liability Policy which provides cover to the University for harm which comes about through the University's, or its staff's, negligence in relation to the design, management or conduct of the study. No arrangements for cover for non-negligent harm will be included.

Post-Study Care

Following the end of study, participants will undergo no further study assessments or procedures but will continue to receive routine clinical care from their direct care team.

Dissemination Policy

To communicate with academics and medical professionals, the intention will be to publish a number of scientific papers in peer-reviewed publications (open-access) and also to present lectures and posters at national and international academic conferences. The results will be used to curate a dataset repository and will be included in the AGI process to harmonize study protocols.

The study will be publicized on a number of partner and charity websites including AFAF, Ataxia Global Initiative (AGI), and Ataxia UK. Social media platforms may also be used to communicate research developments and to stimulate interest and communication amongst patient groups, academics, and the public.

At the end of the study and once results are available participants will be contacted directly by letter to thank them for their participation and to inform them of the study results. Any communications aimed at potential study participants and their families will be submitted for ethical review and approval before dissemination

References

- 3. Jacobi H, du Montcel ST, Bauer P, et al. Long-term disease progression in spinocerebellar ataxia types 1, 2, 3, and 6: a longitudinal cohort study. The Lancet Neurology. 2015/11/01/2015;14(11):1101-1108. doi:https://doi.org/10.1016/S1474-4422(15)00202-1

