Evaluating adult FA patients who have longer disease duration is important, as they may have developed adaptive / compensatory changes, compared to the paediatric population. More recently, wearable sensors are emerging as promising tools for monitoring real-world mobility. Wearable sensors offer a number of advantages compared to laboratory-based assessments, including better tolerability, ecological validity and a more economical approach to patient monitoring, demonstrating huge translational potential to be incorporated in clinical practice in the future. Such an approach promotes inclusivity by enhancing access to healthcare and clinical management through remote monitoring (i.e. rural and underserved populations, and during the pandemic). Two recent publications have highlighted the feasibility and reliability of capturing discriminative gait outcomes in patients with spinocerebellar ataxia and other genetic subtypes using wearable sensors (inertial measurement units) in a supervised environment (14, 15) and real-life habitual environments (14), and these measures correlated with disease severity.

From these studies, it is indisputable that there is a need for more robust studies to compare the efficacy of different assessment tools in measuring the severity of gait and mobility in FA patients.

Objectives and Outcome Measures

The primary outcome measures are instrumented measures of balance and gait collected in a specialist gait laboratory. Data acquisition techniques include stabilometry (force plate analysis), instrumented walkway (GaitRite) and wearable sensors (Opal and Ax6).

Primary Objective

• Evaluate instrumented measures of balance and gait in a controlled setting (clinical research laboratory) repeatedly (three times in 12 months) in ambulatory patients (age 14-65 years) with FA to determine which outcomes are sensitive to disease progression.

Secondary Objectives

- Investigate the influence of sensor location and configuration (i.e. single sensor vs.
 multiple sensors) on the generation of balance and gait outcomes in a controlled setting
 (clinical research laboratory).
- Validate gait outcomes measured using the wearable sensors against a gold standard (instrumented walkway) in a controlled setting (clinical research laboratory)

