- Determine the feasibility of monitoring real-world mobility (habitual activity and gait) in FA patients and explore whether these outcomes are more sensitive than traditional clinical rating scales and controlled laboratory-based assessments.

Study Design and Setting

This study is designed as an observational pilot study involving 16 FA patients (ages 14-65 years). It is sponsored by Newcastle University but will take place at The Newcastle upon Tyne Hospitals NHS Foundation Trust (study site). The study will involve participants visiting at three time-points (Baseline, Month-6, and Month-12).

This protocol is part of a larger collaborative project also involving data collected via a separate study undertaken and managed by the Hertie Institute for Clinical Brain Research and Centre for Integrative Neuroscience (Tubingen).

Data (in an anonymised and pseudo-anonymised form) from both studies will be shared between collaborators and combined for data analyses.

Study Procedures

Participant Identification

Participants will be identified via neurology, paediatric and cardiology clinics at the Newcastle upon Tyne Hospitals NHS Foundation Trust. The direct clinical care team (of which the research team are part) will review clinic lists to identify potentially eligible patients.

Potentially eligible patients will be sent a study invitation letter along with a copy of the relevant Participant Information Sheet (PIS) or will be contacted by telephone/in person by their direct clinical care team (i.e. during a routine clinic) and invited to participate. Patients who are sent an invitation letter by post may also be contacted by telephone after the letter has been sent to check that it has been received.

The study will also be advertised via the websites and social media channels of charities and patient groups (e.g. Ataxia UK) and any volunteering participant will be able to contact the study team for enquiries regarding the study.

Where the age of the eligible participant is 14 or 15-years-old (i.e. under 16), parents/carers with parental responsibility will be provided with information about the study and the opportunity to ask questions about the participation of their child. The potential paediatric participant will also be provided with a suitable Participant Information Sheet (PIS).

Screening and Informed Consent

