Footfalls captured by the instrumented walkway will be processed and a battery of spatio-temporal gait outcomes will be extracted.

The following outcomes will be generated:

- Step length: distance in the direction of travel from the heel during foot contact to the contralateral heel during the next foot contact.
- Step time: duration from foot contact to contralateral foot contact
- Step velocity: step length divided by step time
- Stance time: duration from foot contact to when the foot is lifted off the ground
- Swing time: duration from when the foot is lifted off the ground to its next contact with the ground Step width: perpendicular distance between the heel (foot contact) and the direction of travel of the contralateral foot.

The mean, variability, and asymmetry of gait characteristics will be calculated. Custom algorithms developed at Newcastle University and Tubingen will be used to extract the same spatio-temporal gait outcomes outlined above (barring step width and step width variability) from the wearable sensors.

The gait assessments within the gait lab will be captured on video for the purposes of data veracity (to check for any anomalies in the data) during the processing/data analysis phase.

Habitual physical activity (real world activity) in the community will be measured by using a non-intrusive sensor (Axivity Ax6) on the lower back for seven consecutive days. A custom medical grade fixing is used to adhere the sensor to the skin (figure above). Previously tried and tested documents containing information and guidance will be provided to participants. The sensor will be set to pre-record for seven consecutive days to ensure a representative window of activity covering both weekday and weekend activity is obtained and given to the participant at the end of the laboratory session.

Following completion of recording, participants will return the sensor using a pre-paid, tracked envelope. Data will be downloaded from the sensor for processing. Outcomes of interest include daily time spent supine, sitting and moving as well as specific features of gait as outlined above (i.e. including walking speed, gait variability and asymmetry). We will compare this one sensor approach with the 3-sensor approach in the real-world assessment performed in Tubingen.

Collection of Feedback from Participants

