In addition to the assessments conducted above, at the final study visit (Month-12) participants will be asked to provide feedback on their participation in the study. This will include their overall experience of the study and will also include discussion of any obstacles or challenges around use of wearable sensors. Information obtained from this feedback will be used to improve future studies.

Schedule of Events

	Assessments	Baseline	Month-6	Month-12
			(+/ -2 weeks)	(+/ -2 weeks)
	Eligibility Confirmation	X		
	Informed Consent	X		
	Re-confirmation of Consent (verbal)		X	X
Biometric Assessments	Demographics	X	X	X
	Anthropometrics	X	X	X
	Medical History & Concomitant Medications	X	X	X
c A	Review of Existing Medical Records	X	X	X
Siometri	Vital Signs	X	X	X
	Physical Examination	X	X	X
Clinical Eating Scales	FARS	X	X	X
	SARA	X	X	X
	INAS	X	X	X
	CCAS	X	X	X
Participant Reported Outcomes	PROMA	X	X	X
	NeuroQOL	X	X	X
	SF-36	X	X	X
	ABC Scale	X	X	X
	FSS	X	X	X
	FES-I	X	X	X
Eunctional Assessments	9НРТ	X	X	X
	BRAIN	X	X	X
	FGA	X	X	X
Evaluation of Gait and Postural Control	Static balance (stabiliometry) assessment [Force	X	X	X
	plates and wearable sensors (Opal and Ax6)]			
	10 MWT; Self-selected and Fast Pace [GAITRite	X	X	X
	and Wearable Sensors (Opal and Ax6)]			
	6 Minute Walk [GAITRite & Wearable Sensors (Opal & Ax6)]	X	X	X
	Wearable Sensors (Ax6) in Free-Living	X	X	X
	Environment (for 7 days post-visit)			
	Adverse Event Reporting	X	X	X
	Feedback from Participants			X

Note: Participant reported outcome measures are shaded in grey.

End of study

The end of study for each participant will be completion of their Month-12 visit assessments (including collection of real-world activity data via wearable sensor for seven days post visit).

The overall end of study will be defined as the last participant last visit (LPLV). However, analyses of study data will continue after this point.

Statistics

Outcomes generated from clinical rating scales and questionnaires will be collated into a single dataset for subsequent statistical analysis.

Data from this study will also be combined with data provided by Tubingen University collected as part of a separate study utilising a similar protocol.

Determining which outcomes (clinical rating scales, laboratory and real-world monitoring of mobility) are sensitive to disease progression will be achieved by assessing change over time across the 3 time points using ANOVA.

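### The primary outcome is a whole class of roughly 80 to 220 laboratory variables screened by ANOVA in one pooled sample, so some may qualify by chance and the leading response will tend to be overstated

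*Protocol*

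**What the plan says.** The Objectives and Outcome Measures section of the protocol states: "The primary outcome measures are instrumented measures of balance and gait collected in a specialist gait laboratory". It lists force plate, GaitRite walkway and two wearable systems (Opal and Ax6) as the sources. The primary objective is to measure these three times in 12 months "to determine which outcomes are sensitive to disease progression".

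The variables themselves appear in Study Assessments and Data Collection, under Evaluation of Postural Control, Gait and Habitual Physical Activity. There are five sway outcomes in five stance conditions, and six gait characteristics in three walking tasks. For gait, "The mean, variability, and asymmetry of gait characteristics will be calculated". The wearables are to yield the same gait outcomes apart from step width, and balance outcomes as well.

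The Statistics section decides which outcomes are sensitive by "assessing change over time across the 3 time points using ANOVA". The same method covers clinical scales and real-world measures. The planned UK sample is 16, in a study described as an observational pilot. The Statistics section adds: "Data from this study will also be combined with data provided by Tubingen University". The Tübingen number is not given. The protocol names no leading variable and no threshold for calling an outcome sensitive.

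**The concern.** As written, the plan gives every laboratory variable equal primary standing, applies an ANOVA to each, and estimates responsiveness from the same patients used to pick the responsive ones. Two things follow. Some variables can pass by chance. The one with the largest observed change will usually look better than it is, because ranking favours variables whose random error ran in the right direction.

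This bears on the study's main product. The Study Summary says the results will lead to recommendations on outcomes, based on sensitivity and reliability. The Background justifies the work by the large samples that rating scales require in trials. If responsiveness is overstated and later used to size a trial, that trial would be too small. The four listed clinical rating scales pass through the same ANOVA, so setting the best of many instrumented variables against a few scales would also favour instrumentation through selection alone.

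**Working it through.** **No figure to reproduce.** The protocol gives 16 as the planned size without alpha, power or effect size.

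**Step 1: count the variables.**
- Force plate: 5 sway outcomes × 5 stances = 25.
- Walkway: 6 characteristics × 3 statistics × 3 tasks = 54.
- Subtotal: 25 + 54 = 79. Dropping step-width asymmetry in three tasks gives 76. Collapsing the walking tasks gives 25 + 18 = 43.
- Each wearable system: gait 5 × 3 × 3 = 45, balance 25, so 70. One system gives 79 + 70 = 149; two give 79 + 140 = 219.
- If the wearables contribute gait only, 79 + 2 × 45 = 169.

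**Step 2: expected chance findings.** Assume p < 0.05 counts as sensitive and that nothing truly changes. The expected number is 0.05 × m, whatever the correlation or sample size: 0.05 × 79 = 3.95 and 0.05 × 219 = 10.95. If outcomes were independent, P(at least one) = 1 − 0.95^79 = 98.3%, and above 99.9% for 219.

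**Step 3: allow for correlation.** A three-visit repeated-measures ANOVA was simulated with n = 16, equal correlation between outcomes, no true change and 500 replicates per scenario.

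| Correlation | 79: P(at least 1) | 79: median | 219: P(at least 1) | 219: median |
|---|---|---|---|---|
| 0 | 0.99 | 4 | 1.00 | 11 |
| 0.3 | 0.91 | 3 | 0.99 | 8 |
| 0.5 | 0.75 | 2 | 0.89 | 5 |
| 0.7 | 0.43 | 0 | 0.61 | 1 |
| 0.9 | 0.26 | 0 | 0.29 | 0 |

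The mean stays near 4 or 11, but at high correlation most replicates give none and a few give many.

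**Step 4: the top-ranked response.** The standardised response (SRM) is the mean baseline-to-Month-12 change divided by its SD. Every true SRM is set to 0.3. The table gives the average of the largest absolute observed SRM. The pooled n = 32 is illustrative only.

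| Correlation | n=16, 79 | n=16, 219 | n=32, 79 | n=32, 219 |
|---|---|---|---|---|
| 0 | 1.08 | 1.24 | 0.80 | 0.89 |
| 0.5 | 0.88 | 0.98 | 0.66 | 0.72 |
| 0.9 | 0.55 | 0.64 | 0.46 | 0.49 |

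Inflation at n = 16 runs from 0.55/0.3 = 1.8 to 1.24/0.3 = 4.1. At n = 32 it runs from 0.46/0.3 = 1.5 to 0.89/0.3 = 3.0.

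**Step 5: effect on a later trial.** Required size scales with 1/SRM². At n = 16 with 79 outcomes and correlation 0.6 to 0.3, the top SRM averages 0.81 to 0.97, so the shortfall is (0.81/0.3)² = 7.3 to (0.97/0.3)² = 10.5. At correlation 0.9 and n = 16 it is (0.55/0.3)² = 3.4 to (0.64/0.3)² = 4.6.

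If true SRMs vary between outcomes (assumed mean 0.3, SD 0.2) and correlation is 0.3 to 0.6, the winner's shortfall falls to 2.8 to 4.1 at n = 16 and 1.7 to 2.2 at n = 32. The overstatement of the response itself is then √2.8 = 1.7 to √4.1 = 2.0 at n = 16, and √1.7 = 1.3 to √2.2 = 1.5 at n = 32.

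**The case against.** The strongest reply is that this is a pilot whose stated purpose is to find the responsive outcomes. Screening widely is legitimate, and fixing two or three variables first would presuppose the answer. That stands, and it is why a short primary list is not required below.

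A second reply is that multiplicity rules and bootstrap methods usually sit in a statistical analysis plan, which may exist unseen. That also stands as far as it goes: their absence is not an error. What the protocol does fix is the breadth of the primary class and the ANOVA rule.

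Third, sensitivity is not the only basis for recommendation. The Study Summary adds reliability, and the Statistics section plans test-retest reliability and agreement with the walkway. This tempers the selection. It does not remove it, because a reliable variable can still owe part of its observed change to chance.

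Fourth, the upper count is partly our reading. The protocol does not say that all five sway outcomes come from each wearable. The 79 from force plate and walkway needs no such assumption.

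Finally, the disease progresses, so the no-change case is a benchmark and not a forecast. Step velocity is computed from step length and step time, and the wearables re-measure the same walks, so high correlations are plausible.

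**Conclusion.** The concern holds in a limited form. The plan screens 79 laboratory variables (43 on the narrowest count, about 219 on the widest) and states no error control. About 4 of 79 or 11 of 219 would qualify on average if none changed, given an assumed 5% threshold. The leading response would be overstated about 2- to 4-fold at n = 16, or 1.5- to 3-fold at an assumed pooled n = 32, if all true responses were 0.3. The overstatement is smaller if true responses differ.

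A reader might infer three stronger claims that the documents do not support:
- **That the analysis rests on 16 people.** The protocol pools them with Tübingen, so the analysed number is larger by an unknown amount. Pooling reduces the inflation but leaves the expected number of chance findings unchanged.
- **That several outcomes are bound to qualify by chance.** No threshold is stated, some outcomes may truly change, and at correlation 0.7 the median number among 79 is zero.
- **That a later trial would be 7 to 10 times too small.** That needs n = 16, one common true response of 0.3, correlation of 0.3 to 0.6, and a trial sized on the largest observed effect, which the protocol does not propose.

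This is a worthwhile, inexpensive improvement and does not invalidate the design.

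**What to change.** In the Statistics section:
1. State that the instrumented laboratory outcomes form one screening family, list its members, and apply Benjamini-Hochberg false-discovery control across it.
2. Report the standardised response with a confidence interval for every outcome in the family, whether or not it is selected.
3. For any outcome recommended, give a bootstrap optimism-corrected response, repeating the whole selection in each resample, and show Newcastle and Tübingen estimates separately so that each site checks the other.

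Naming a few key outcomes before the longitudinal data are analysed would sharpen the message, but it is optional and the investigators' choice.

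The cost is a few sentences of protocol text and some extra analysis, with no added measurement or patient burden. The downside is that fewer outcomes will be called sensitive and the quoted effects will be smaller. Power is already modest: at n = 16 a single unadjusted ANOVA detects a true response of 0.3, 0.5 or 0.8 with probability of about 16%, 38% or 78%. This is a further reason to rest recommendations on estimates and intervals more than on which outcomes pass.

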- Willing to wear a small sensor on the lower back for seven consecutive days
- No other known neurological or musculoskeletal disorder affecting balance and mobility.

Exclusion criteria

- Lacking capacity to provide informed consent
- Enrolled in interfering therapy or clinical drug trial currently or within last three months
- Pregnancy at the time of enrolment
 Any other reason, which in the opinion of the recruiting investigator would preclude involvement in the study

• Withdrawal Criteria

- Participants have the right to withdraw from the study at any time. A member of the research team should try to ascertain the reason for withdrawal and document this reason within the participant's medical records.
- The Investigator may discontinue a participant from the study at any time if the Investigator considers it necessary for any reason including:
 - Participant withdrawal of consent
 - Significant protocol deviation or non-compliance
 - Investigator's discretion that it is in the best interest of the participant to withdraw
 - An adverse event that renders the participant unable to continue in the study*
 - Termination of the study by the sponsor or funder

If participants are withdrawn from the study, the information already obtained up to point of withdrawal will be retained. To safeguard the rights of the participant, the minimum of personally-identifiable information possible will be used.

Participants who withdraw from the study at any point after Baseline will not be replaced.

*Please note, if the participant has a severe adverse reaction to the adhesive used to attach the wearable sensor- further use of wearable sensors in the home environment may be stopped however the participant will still be able to remain on the study and complete the other assessments.

Study Assessments and Data Collection

Each participant will undergo the following assessments at three visits (Baseline, at Month-6 +/- 2 weeks, and at Month-12 +/- 2 weeks). Unless specified otherwise, all activities will be conducted for all participants.

Biometric Assessments

- Demographics (age, sex, alcohol consumption, smoking status, ethnicity, education level, socio-economic status)
- Anthropometrics (weight, height, body mass index)
- Medical history and concomitant medications
- Physical examination and vital signs (including blood pressure, pulse rate, respiratory rate)
- Clinical review of medical records and collection of previous/existing results from the following

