 - Disease onset and year of diagnosis
 - Molecular genetic test (specifically the number of GAA repeat in *FXN* gene or point mutation)
 - Neuroimaging (CT or MRI head)
 - Laboratory tests (e.g. HbA1c and CK)
 - Nerve conduction study and electromyography (evidence of neuropathy/ganglionopathy)
 - Cardiac investigations such as ECG, echo radiography and cardiac MRI where available

Clinical Rating Scales

- Friedreich ataxia rating Scale (FARS)
- Scale for Assessment and Rating of Ataxia (SARA)
- Inventory of non-ataxia signs (INAS)
- CCAS (Cerebellar Cognitive Affective/ Schmahmann Syndrome Scale)

Participant Reported Outcomes

(Participant Reported Outcomes may be completed online or on paper up one week before or after the visit date)

- PROMA (Patient Reported Outcome Measure of Ataxia)
- NeuroQoL
- SF-36 (36-Item Short Form Survey Instrument)
- ABC Scale (Activity-Specific Balance Confidence Scale)
- FES-I (Falls Efficacy Scale International)
- The Fatigue Severity Scale (FSS)

Functional Assessments

- 9-hole peg test (9HPT)
- BRadykinesia Akinesia INcoordination (BRAIN) test
- Functional gait assessment (FGA)

Evaluation of Postural Control, Gait and Habitual Physical Activity

Wearable sensors comprising of triaxial accelerometers and gyroscopes (Opal, Axivity AX6) will be attached to the lower back and ankles for assessments in a specialist gait laboratory.

[figure not shown]

Figure. Wearable sensors. (A) Single sensor (Axivity AX6). (B) Opal sensors.

Postural control will be assessed with participants standing still under a variety of conditions that challenge balance:

- Normal stance (10-cm distance between heels), eyes open and eyes closed
- Narrow stance (feet together), eyes open and eyes closed
- Semi-tandem stance, eyes open

Participants will stand on a force platform for up to 60-seconds depending on functional mobility in each condition. Custom algorithms and manufacturer software will be used to derive balance outcomes from the force platform and wearable sensors respectfully. Outcomes extracted include centre of pressure area, displacement, path length, velocity, and root mean square.

Gait assessment will be completed using an instrumented walkway within a 10-m straight walkway. As functional mobility allows participants will be asked to complete:

- 6x 10-metre intermittent walks at a self-selected normal pace,
- 4x 10-metre walks at a self-selected fast pace
- 6-minute walk

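### The three-visit ANOVA named for the primary objective ignores the order and direction of change; a prespecified slope or 12-month change from a mixed model answers the question better at almost no cost

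*Protocol*

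**What the plan says.** The Primary Objective is to measure balance and gait three times in 12 months "to determine which outcomes are sensitive to disease progression". The Statistics section gives one method for this: it "will be achieved by assessing change over time across the 3 time points using ANOVA". The same sentence covers clinical rating scales, laboratory measures and real-world monitoring. It does not say which form of ANOVA is meant, which contrast decides the matter, or how incomplete data are treated. Effect sizes are mentioned only for the comparison of sensor location and configuration.

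Three other statements bear on the data that will reach this analysis:

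- Withdrawal Criteria: "Participants who withdraw from the study at any point after Baseline will not be replaced". They also say that "the information already obtained up to point of withdrawal will be retained".
- Study Assessments and Data Collection, on the gait tasks: "As functional mobility allows participants will be asked to complete" the walks.
- Statistics: the data will be combined with Tübingen data "collected as part of a separate study utilising a similar protocol". The Tübingen sample size is not given. The planned UK sample is 16.

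**The concern.** Progression has an order and a direction: Month 12 should be worse than Month 6, and Month 6 worse than Baseline. The overall F-test across three visits spreads its sensitivity over every pattern of difference, including a rise and return. That has two consequences for a study meant to rank outcome measures. Power is spent on patterns that are not progression. And an outcome with a temporary Month-6 shift, such as a practice effect on a repeated task, can pass as sensitive to progression.

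A third consequence is conditional. The same people are seen three times, so repeated-measures ANOVA is the natural reading, and its classical form needs all three visits for the outcome being analysed. Since gait tasks depend on what the participant can still do, gaps may be related to worsening. If so, the participants left out would tend to be those who declined most.

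**Working it through.** The protocol gives no alpha, power, effect size, SD or dropout rate for this analysis, so there is no stated figure to reproduce. The only input from the document is n = 16 with three visits. The rest is assumed: two-sided alpha 0.05, compound symmetry, linear decline, and d = mean 12-month change divided by the SD of that change, over a range of 0.3 to 1.0.

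**Power.** Under compound symmetry, set the SD of change to 1, so the within-person variance is 0.5. Visit means are 0, d/2 and d, and the squared deviations from their mean sum to d²/2. The noncentrality is λ = n × (d²/2) / 0.5 = n d². For n = 16 and d = 0.6, λ = 16 × 0.36 = 5.76. All three tests have this λ and differ only in degrees of freedom: F(2, 30) for the ANOVA, F(1, 30) for the linear contrast, and F(1, 15) for the paired 12-month contrast.

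| d | ANOVA, 2 df | Paired 12-month contrast | Linear contrast |
|---|---|---|---|
| 0.3 | 16% | 20% | 21% |
| 0.5 | 38% | 47% | 49% |
| 0.6 | 52% | 61% | 64% |
| 0.75 | 73% | 80% | 83% |
| 1.0 | 94% | 96% | 97% |

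At d = 0.6 the ANOVA gives up 9 points (61 − 52) to 12 points (64 − 52).

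**Month-6-only shift.** Means are 0, d and 0, so there is no net 12-month change. The squared deviations sum to (2/3)d², and λ = n × (2/3)d² / 0.5 = (4/3) n d². For n = 16 and d = 0.5, λ = (4/3) × 16 × 0.25 = 5.33. The ANOVA is significant in 49% of studies (85% at d = 0.75). The linear or 12-month contrast stays at its nominal 5%. A larger pooled sample makes this worse: at an assumed n = 32, the 0.5 shift is flagged in 82%.

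**Missing visits.** If 10% were missing at each follow-up visit (assumed), complete cases would be 16 × 0.9² ≈ 13. With n = 13 and d = 0.6, λ = 13 × 0.36 = 4.68 and ANOVA power is 43%.

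Bias was checked by simulating 200,000 participants with intercept SD 1, mean 12-month change 0.60 with slope SD 0.6, error SD 0.3, and 18% to 25% missing at Month 12.

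| Missingness at Month 12 driven by | Complete cases | Likelihood model, all visits |
|---|---|---|
| chance | 0.60 | 0.60 |
| observed Month-6 level | 0.57 | 0.60 |
| observed Month-6 worsening | 0.42 | 0.60 |
| unobserved Month-12 worsening | 0.42 | 0.50 |

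The complete-case shortfall runs from none to about 30% (0.18 / 0.60). A separate simulation of studies of 16 (slope SD 0.5, error SD 0.3) let missingness follow the Month-12 level itself, which is closest to being unable to do the task that day. Against a true change of 0.60 in size, complete cases gave 0.51 and the likelihood model 0.52.

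**The case against.** The strongest reply is that the protocol names a method in one sentence, that its form, contrasts and missing-data rules may sit in an SAP that is not shown, and that this is an observational pilot supported by a biostatistician. Much of this stands, and it rules out several stronger readings:

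- A reader might infer that incomplete participants will be dropped. The protocol does not say so, and it keeps data collected before withdrawal. Deletion is a property of classical repeated-measures ANOVA and would act outcome by outcome: losing the 6-minute walk would not remove the 10-metre data. A one-way ANOVA would keep the data but ignore the pairing, with power of about 11% to 20% for d of 0.5 to 0.75 at an assumed intraclass correlation of 0.8.
- A reader might infer that decline will be understated by some definite amount. No missingness rate or mechanism is given, and under random missingness there is no bias.
- A reader might infer that season produces false positives, because Month 6 falls half a year from the other two visits. The summary allows 24 months overall and 12 per participant, so entry can be spread over about a year. Seasonal shifts then cancel in the mean, and simulation gives the nominal 5% rejection. Inflation would need clustered recruitment, which the protocol does not describe.
- A reader might fault the lack of a centre term in the pooled analysis. Silence on a covariate is missing detail, and the protocol does not say the centres will be pooled unadjusted.

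The power figures also use 16, whereas the pooled sample will be larger. The absolute values are therefore lower bounds as far as sample size goes.

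What the reply does not meet is the choice of target. The protocol states the method by which sensitivity to progression will be determined, and an SAP would be expected to elaborate that method. Inspecting the mean profile could reveal direction, but the stated rule does not use it. Pooling raises power without making the test directional.

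**Conclusion.** The point holds as an inexpensive improvement to the stated analysis of the primary objective. It does not make the study invalid. The firm part is that a three-visit overall test does not target ordered decline. At n = 16 and an assumed standardised change of 0.6, it costs 9 to 12 points of power against a one-degree-of-freedom contrast. It would also flag an assumed shared Month-6 shift of 0.5 SD in 49% of studies with no net change. These sizes rest on linear decline, compound symmetry and alpha 0.05, and the protocol documents no such Month-6 shift. The conditional part is that, if classical repeated-measures ANOVA is used and gaps follow worsening, decline can be understated. How far depends on a rate and mechanism that the protocol does not give.

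**What to change.** In the Statistics section, replace the ANOVA sentence with the following:

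- A linear mixed model for each outcome, using all available visits.
- Sensitivity to progression judged on one prespecified quantity, either the slope or the Baseline-to-Month-12 change, in the expected direction. Report it for each outcome with a 95% confidence interval and a standardised response mean, so that outcomes can be compared.
- Month 6 used to check the shape of change, and not as evidence of progression on its own.
- The reason recorded when a task is not done, with a sensitivity analysis for tasks not done because of ataxia. This is needed because the mixed model only partly corrects gaps driven by unobserved Month-12 status.

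The cost is a few sentences and a little more analysis work, with no added visits or participants. The price in performance is less sensitivity to non-monotone change, which is acceptable when the question is progression.
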